DURATION OF SUBJECT PARTICIPATION AND STUDY DURATION	2 years. 18 months of active patient's study participation; 21 total months in the field including screening, enrollment, follow-up and data analysis.
FOLLOW-UP	2 weekly follow up visits from enrollment to 28 weeks gestation followed by weekly visits till delivery

LIST OF TABLES

Table 1 STUDY OUTLINE	26
Table 2 ASSESSMENT SCHEDULE	27

LIST OF FIGURES

Figure 1 PIPSICKLE Trial flowchart	21
--	----

LIST OF ABBREVIATIONS AND ACRONYMS

AE	Adverse event
CRF	Case report form
CRA	Clinical research associate
CMUL	College of Medicine, University of Lagos
CI	Confidence interval
GCP	Good Clinical Practice
Hb	Haemoglobin
IUGR	Intrauterine growth restriction
LASUTH	Lagos State University Teaching Hospital
LBW	Low birth weight
LDA	Low dose aspirin
LUTH	Lagos University Teaching Hospital
ML	Machine learning
OR	Odds ratio
PACTR	Pan Africa Clinical trials Registry
PE	Preeclampsia
RCT	Randomised controlled trial.
SAE	Serious adverse event
SCD	Sickle cell disease
HbSS	Sickle cell Anaemia
HbSC	Sickle Hb C disease
SDG	Sustainable Development Goal
TETFund	Tertiary Education Trust Fund
WHO	World Health Organization
AE	Adverse Event
SAE	Serious Adverse Event
SOP	Standard Operating Procedure
DSMC	Data and Safety Monitoring Committee

CONFIDENTIAL

GCP Good Clinical Practice
IRB Institutional Review Board

GLOSSARY OF TERMS

Assessment	A procedure used to generate data required by the study
Control (Placebo) drug	A study drug used as a comparator to reduce assessment bias, preserve blinding of investigational drug, assess internal study validity, and/or evaluate comparative effects of the investigational drug.
Investigational (Active) drug	The study drug whose properties is being tested in the study.
Study drug	Any drug (control or investigational) administered to the patient as part of the required study procedures; includes investigational drug and any control drugs
Enrollment	Point/time of patient entry into the study; the point at which informed consent must be obtained (i.e. prior to starting any of the procedures described in the protocol)
Medication number	A unique identifier on the label of each medication package.
Study ID	A number assigned to each patient that is enrolled into the study. When combined with the center number, a unique identifier for each patient in the study is created. This is done automatically during the randomisation process.

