3.2 Sample Population

A total of 476 eligible pregnant HbSS and HbSC women from 12-28 weeks gestation will be enrolled and followed until delivery. Two study groups will comprise of approximately 238 HbSS or HbSC pregnant women who are confirmed with Haemoglobin phenotype testing by HPLC randomly assigned to each arm.

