3.4 Randomisation (Interventions: Investigational and placebo therapy)

This study will employ a randomised, patient and investigator-blinded, multi-centre, parallel-group, placebo controlled design to assess efficacy, safety and tolerability of Low dose aspirin for preventing intrauterine growth restriction and preeclampsia in sickle cell pregnancy (PIPSICKLE).

At the baseline visit, a pregnant woman who is referred or is found to have sickle cell disease (HbSS or HbSC) on routine haemoglobin genotype testing, meets the eligibility criteria and gives informed consent will be enrolled and randomised to one of the two treatments groups (Blinded)

Randomisation and allocation concealment will be done with the use of a web-based randomisation software known as ‘Sealed envelope’ in a 1:1 ratio in blocks stratified according to centre. Only an unblinded pharmacist will be aware of the actual codes and the pharmacist will not be in contact with any of the study participants or investigators.

A total of 476 eligible pregnant HbSS and HbSC women will be randomly assigned to either group.

Those in the LDA group will receive 100mg aspirin daily while those in the placebo group will receive a tablet that looks like the active drug in terms of diameter, thickness and colour.

The drugs will be started between 12 and 28 weeks’ gestation and continued till 36 weeks or delivery, whichever comes earlier.

The study drugs will be prepared in sachets and dispensed in 2 weekly doses (*3 weeks dosage at enrollment*). The women will be sent daily reminders by text message, questioned on compliance at each visit and asked to bring in their used sachets for sighting. All the women will be followed from enrollment till delivery.

The study drugs will be packed in boxes labelled with codes and each box will have sufficient study drugs for one patient for 24 weeks with 4 extra weeks’ worth of drug in case the patient loses some pills. The drug boxes will be delivered to each centre in batches of 8 (4) and 4 (2) more boxes will be sent to the centre whenever a message is received from the centre that there are 4 boxes left.

In the unlikely event that a woman loses all her drugs, the unblinded pharmacist will be asked to label another batch for the woman, based on the code list that she holds. If all the relevant drugs have been used up, the trial pharmaceutical company Emzor Pharmaceutical Ltd, will be asked to produce a new pack of study (investigational or control) drug.

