5.5 Study Completion visit (Pregnancy loss or delivery)

A participant will be considered to have completed the study once there is a pregnancy loss or delivery at any time after randomisation and all relevant data is captured into the appropriate study completion CRF.

The following steps will be taken at the end of study visit

- ❖ Physical examination
- ❖ Evaluate compliance & ADE
- ❖ Complete all relevant documents
- ❖ Complete delivery e-CRF (*at delivery- Appendix viii*) and end of study visit e-CRF at completion of all study visits and data entry (*Appendix ix*) and other relevant source documents.

- ❖ Counselling and necessary referral (e.g Postpartum and family planning clinics)

Tables below lists all of the assessments and indicates with an “X” the visits when they are performed. All data obtained from these assessments must be supported in the patient’s source documentation. The Table indicates which data are entered into the database (D) or remain in source documents only (S) or both (SD).

Assessments that generate data for database entry and which are recorded on CRFs are listed using the CRF name (Enrollment, Visit, Study completion). Assessments that are transferred to the database electronically (e.g. laboratory data) are listed by test name.

Table 1: Study Visit Schedule

	Pre-treatment	Treatment (Enrollment and follow-up)																			Delivery			
Study Visit	0	1	2	3	4	5	6	7	8	9	10	11	12	13	14	15	16	17	18	19	20	21		
GA in weeks	6-11	12	14	16	18	20	22	24	26	28	29	30	31	32	33	34	35	36	37	38	39	40		
Screening	X	X	X	X	X	X	X	X	X															
Enrollment		X	X	X	X	X	X	X	X	X														
Follow-up			X	X	X	X	X	X	X	X	X	X	X	X	X	X	X	X	X	X	X	X	X	
End of study				X	X	X	X	X	X	X	X	X	X	X	X	X	X	X	X	X	X	X	X	

Table 2: Assessment schedule for study participants

Phase	Pre-Treatment	Treatment (Enrollment and follow-up)																	Delivery			
Study visit	0	1	2	3	4	5	6	7	8	9	10	11	12	13	14	15	16	17	18	19	20	21
GA in weeks	6-11	12	14	16	18	20	22	24	26	28	29	30	31	32	33	34	35	36	37	38	39	40
Inclusion/exclusion criteria (S)	X	X	X	X	X	X	X	X	X													
Written informed consent (S)	X	X	X	X	X	X	X	X	X													
Demographics/ PMH (SD)	X	X	X	X	X	X	X	X	X													
Concomitant medication (SD)	X	X	X	X	X	X	X	X	X	X	X	X	X	X	X	X	X	X	X	X	X	X
Body weight (SD)	X	X	X	X	X	X	X	X	X	X	X	X	X	X	X	X	X	X	X	X	X	X
Physical examination (SD)	X	X	X	X	X	X	X	X	X	X	X	X	X	X	X	X	X	X	X	X	X	X
Laboratory (SD) Hb +Urinalysis	X	X	X	X	X	X	X	X	X	X	X	X	X	X	X	X	X	X	X	X	X	X

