7.7 Study drug discontinuation

Study drug must be discontinued for a given patient if the investigator determines that continuing it would result in a significant safety risk for that patient. The following circumstances require study drug discontinuation:

- Emergence of severe adverse events: severe nausea/vomiting, allergy, severe pruritus, life threatening symptoms
- Persistent or heavy vaginal bleeding
- Abnormal laboratory values: Platelet count $\leq 50 \times 10^9/\text{ml}$
- In addition to these requirements for study drug discontinuation, the investigator should discontinue the study drug for a given patient if, on balance, he/she thinks that continuation would be detrimental to the patient's well-being.

Patients who discontinue study drug will be followed for the whole study duration until 36 weeks or delivery at which time all of the assessments listed for the final visit will be performed.

Reasons for Study Drug discontinuation should be completed, giving the date and primary reason for stopping the study drug under the relevant portion of the CRF.

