5.2 Analysis Populations

5.2.1 Intention to Treat (ITT) population

- The intention to treat population refers to all subjects who were randomised. Following the intention-to-treat principle, patients will be analysed according to the treatment they were assigned to at randomization.

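### Protocol 7.7 lets follow-up of women who stop study drug end at 36 weeks, contradicting the follow-up to delivery that the primary outcome needs

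*Protocol*

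**What the plan says.** Protocol 7.7 lists the circumstances in which study drug must be stopped, then sets the follow-up of the women concerned: "Patients who discontinue study drug will be followed for the whole study duration until 36 weeks or delivery". The section puts their closing assessments at that same point. It does not say whether the earlier or the later of the two times applies.

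Elsewhere the end point is delivery, with no exception for women off drug:

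- Protocol 3.2: "A total of 476 eligible pregnant HbSS and HbSC women from 12-28 weeks gestation will be enrolled and followed until delivery".
- Protocol 3.4: "All the women will be followed from enrollment till delivery".
- Protocol 5.5: "A participant will be considered to have completed the study once there is a pregnancy loss or delivery at any time after randomisation".
- Protocol synopsis, follow-up row: "2 weekly follow up visits from enrollment to 28 weeks gestation followed by weekly visits till delivery".
- SAP Table 3 measures follow-up duration from randomisation to delivery or miscarriage.

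The 36-week limit appears in Protocol 3.4 as the end of dosing. There the drugs are "continued till 36 weeks or delivery, whichever comes earlier".

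Two other places bear on the same women. Protocol 6.1 lists stopping study drug among the reasons for which a patient must be withdrawn, and the glossary says that no further assessments are planned after premature withdrawal. The glossary also says that stopping drug and withdrawing need not coincide.

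On the analysis side, SAP 5.2.1 says "The intention to treat population refers to all subjects who were randomised", and SAP 5.4 rules out imputation of endpoints in the main analysis.

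**The concern.** The primary composite is IUGR (from birthweight), perinatal death or miscarriage. Birthweight exists only at delivery, and the SAP's perinatal death runs to the end of the first week of life. A woman whose last assessment is at 36 weeks, still pregnant, has no birthweight, and her outcome from 36 weeks onward is unknown.

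The loss would not be random. Among women who stop drug, those whose pregnancies end before 36 weeks, including every miscarriage, would keep their outcome. Those whose pregnancies continue would lose it. Stopping could also differ by arm. Persistent or heavy vaginal bleeding is a stopping criterion in 7.7, and SAP 2.2 lists vaginal bleeding as a potential adverse effect. If so, a complete-case comparison would no longer be the randomised one, even though the analysis set is defined as everyone randomised.

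**Working it through.** **1. The passages side by side**

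| Place | End of follow-up | Exception for women off drug? |
|---|---|---|
| Protocol synopsis | Delivery | No |
| Protocol 3.2 | Delivery | No |
| Protocol 3.4 | Delivery (dosing ends at 36 weeks or delivery, the earlier) | No |
| Protocol 5.5 | Delivery or pregnancy loss | No |
| SAP Table 3 | Delivery or miscarriage | No |
| Protocol 7.7 | 36 weeks or delivery, which one not stated | Applies only to them |
| Protocol 6.1 with glossary | Withdrawal, then no assessments | Applies to them |

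Women who stop drug therefore have three different end points.

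**2. Which reading of 7.7 is more natural**

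- Later of the two: a woman who delivers at 32 weeks would be followed to the 36th week of a pregnancy that has ended.
- Delivery always: the mention of 36 weeks does nothing.
- Earlier of the two: the 36-week limit has a function, and the phrase matches the dosing limit in 3.4.

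The third reading is the easiest to take from the sentence. Against it, the same sentence also speaks of the whole study duration, and 5.5 places completion at delivery or loss. The text is ambiguous.

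**3. What would be lost on the earlier-of reading**

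The delivery e-CRF (Appendix 08) holds the date and gestation of delivery, birthweight, and fetal outcome including early neonatal death. It cannot be completed for a woman who is undelivered at her last visit. A fetal death from 28 weeks up to her 36-week visit would still be known.

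**4. How many outcomes**

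The plan's own figures come first: 396 × 1.20 = 475.2, rounded up to 476, so the attrition margin is 476 − 396 = 80 women. The target of 396 is taken as stated. (The pooled two-sided formula for 20% against 10% at 90% power gives 266 per arm rather than 198. That is a separate matter and does not affect this point.)

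Assumptions, because the documents give neither rate: a fraction d stops drug, and a fraction q = 0.80 of those are undelivered at 36 weeks.

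Outcomes at risk = 476 × d × q

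| d | Women stopping | Outcomes at risk | Share of 476 | Outcomes left |
|---|---|---|---|---|
| 5% | 23.8 | 19 | 4.0% | 457 |
| 10% | 47.6 | 38 | 8.0% | 438 |
| 15% | 71.4 | 57 | 12.0% | 419 |

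Over a wider range, d from 5% to 20% and q from 50% to 90%, the count runs from 476 × 0.05 × 0.50 = 12 to 476 × 0.20 × 0.90 = 86 (2.5% to 18%).

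The SAP's 5% line for missing outcomes (5.4) is 0.05 × 476 = 23.8 women. With q = 0.80 this route alone reaches it when d = 0.05 / 0.80 = 6.25%.

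**5. Power**

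Power = Φ{[Δ − 1.96 √(2p̄(1−p̄)/n)] / √([p₁(1−p₁) + p₂(1−p₂)]/n)}, with p₁ = 0.20, p₂ = 0.10, Δ = 0.10, p̄ = 0.15. At n = 238 per arm this is Φ{(0.10 − 1.96 × 0.0327) / 0.0324} = 86.6%. With n = 238 × (1 − 0.80d), it is 85.2%, 83.6% and 82.0% for d = 5%, 10% and 15%. These figures assume no other loss.

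**6. Selectivity**

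At d = 10% there are about 48 women off drug. About 38 would lose the outcome and about 10 would keep it, and those 10 are exactly the pregnancies that ended before 36 weeks. The attrition allowance replaces numbers and does nothing about this selection.

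**The case against.** The strongest reply is that the plan already follows everyone to delivery. The synopsis, 3.2, 3.4 and 5.5 say so without exception, the visit tables run to week 40, and the delivery form captures birthweight. Section 3.4 keeps dosing and follow-up apart: the words making the earlier time govern belong to dosing there and do not appear in 7.7. Section 7.7 itself refers to the whole study duration.

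This stands to a large extent. A reader might infer that women who stop drug and remain pregnant at 36 weeks have no birthweight or perinatal outcome by rule. The documents do not support that. Section 7.7 is ambiguous, sites that work from 3.4 or 5.5 would collect the outcome, and fetal deaths between 28 and 36 weeks would be recorded on any reading. Nor is there any sign of a deliberate decision to stop at 36 weeks.

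The reply does not remove the contradiction. None of the general passages says that it overrides 7.7, and 7.7 is the section a site would consult when a woman stops drug.

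Two further objections are fair. First, 6.1 with the glossary is the stronger route to lost outcomes, because it ends all assessments at withdrawal. But aligning 6.1 to 7.7 would leave the 36-week wording in place, so both need attention. Second, the all-randomised ITT definition says who is analysed and not for how long they are followed, and SAP 5.4 openly accepts a complete-case analysis. At 5% or more missing it calls for tables of baseline characteristics, with imputation or weighting only to be considered. That does not repair a loss that depends on when the pregnancy ended.

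**Conclusion.** Wrong as written, as an internal contradiction: 7.7 names an end of follow-up for women off drug that conflicts with the synopsis, 3.2, 3.4, 5.5 and the SAP's follow-up variable, and 6.1 with the glossary gives yet another.

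The consequence is conditional. It arises only where a site takes the earlier time in 7.7 and does not go on to collect the delivery outcome. On the assumed rates (5% to 15% stopping, 80% of those undelivered), 19 to 57 of 476 outcomes is an upper limit.

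A reader might infer that the trial loses its power this way. On the plan's own target it does not: 419 to 457 outcomes remain against 396, although the margin of 80 must also absorb every other loss. The main concern is selective loss after treatment stops. Its direction and size cannot be calculated from the documents, since they do not give stopping rates by arm.

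**What to change.** Amend Protocol 7.7 so that outcome follow-up of women who stop study drug runs to delivery or pregnancy loss, in line with 3.4 and 5.5. State that the delivery e-CRF (birthweight, fetal outcome and first-week outcome) is completed whether or not study drug was stopped, unless the woman withdraws consent to follow-up.

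Reconcile 6.1 and the glossary in the same amendment, so that stopping drug does not by itself end outcome collection. Clarify the same phrase in Protocol 9.2, where the Primary Analysis population takes in women who reached 36 weeks or delivery. As worded, a woman could count as complete at 36 weeks with no birth outcome.

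The cost is a short wording amendment with ethics approval under 11.5 and a note to sites. It adds no visits, because the schedule already runs to delivery. It concerns outcome collection only and leaves the drug-stopping criteria unchanged.

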7.8 Emergency unblinding of treatment assignment

- As aspirin is a tried and tested commonly used drug, we do not foresee any need for emergency unblinding. However, in the event of an acute hypersensitivity reaction, we will have to perform emergency unblinding. - - Any other reason as determined by the DSMC/External monitoring committee.

7.9 Treatment exposure and compliance

All medication (other than study drug) and significant non-drug therapies administered after the patient starts treatment with study drug will be documented under concomitant medications/Significant non-drug therapies in the CRF after start of study drug.

Records of study medication used and exact dosages administration and compliance will be kept during the study. Drug accountability will be noted by the field monitor during site visits and at the completion of the study.

8.0 ADVERSE EVENTS AND REPORTING REQUIREMENTS

8.1 Adverse Events (AEs)

- ❖ An adverse event is the appearance or worsening of any undesirable sign, symptom, or medical condition occurring after starting the study drug even if the event is not considered to be related to study drug. Study drugs include the investigational drug/placebo under evaluation that is given during the treatment phase of the study.
- ❖ *Medical conditions/diseases present before starting study drug are only considered adverse events if they worsen after starting study drug.*
- ❖ Abnormal laboratory values or test results constitute adverse events only if they induce clinical signs or symptoms, or are considered clinically significant, or require therapy.

Clinical signs and symptoms will be assessed at baseline, before dosing and all follow-up visits, and recorded on the CRF. Any symptom that worsens or starts after baseline will be recorded as a new adverse event on the e-CRF.

The occurrence of adverse events, such as weakness, chills/rigors, headache, myalgia, dizziness, epigastric pain, abdominal pain, anorexia, nausea, vomiting, diarrhea, palpitations, insomnia, pruritus, coughing, tinnitus, abnormal gait, tremor, clonus or dyskinesia, will be sought by the investigator (or designee) at each study visit and recorded in the e-CRF.

Adverse events also may be detected when they are volunteered by the patient during or between visits or through physical examination, laboratory test, or other assessments.

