3.9 Outcome measures

Primary outcomes:

- Birth weight below 10th centile for gestational age on the WHO INTERGROWTH- 21st birthweight charts
- Stillbirth
- Fetal death
- Miscarriage.

Secondary outcomes:

Pregnancy complications: Pre-eclampsia, Preterm delivery, retained placenta, placental abruption;

Maternal complications: Maternal death, frequency of crises, no of blood transfusions, incidence of urinary tract infection, respiratory tract infection, acute chest syndrome, and potential adverse effects such as vaginal bleeding, epigastric pain and heartburn.

Preeclampsia will be diagnosed based on ISSHP classification (17) if there is development of hypertension (either systolic blood pressure ≥ 140 mm Hg or diastolic blood pressure ≥ 90 mm Hg on two occasions at least 4 h apart) after 20 weeks gestation plus one of the following: proteinuria, thrombocytopenia or any multisystem complication.

Proteinuria will be defined as a dipstick test with $\geq 1+$ proteinuria ($\geq 30 \text{ mg dl}^{-1}$) on two occasions at least 4 hours apart, without any evidence of a urinary tract infection. Or UPCR $>300 \text{ mg/g Cr}$.

Thrombocytopenia will be defined as platelet count $< 100,000/\text{Ul}$.

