8.3 Reporting Adverse Events

Study site coordinators will document on the appropriate study e-CRF all AEs reported by or observed in enrolled study participants regardless of severity and presumed relationship to study product. The study clinician must provide on this form information on symptoms, time of onset, severity, frequency, product-relatedness, actions taken and participant outcome. The PI may request additional information from the site if it is needed to evaluate the AE. Site coordinators will report information on SAEs to the local Ethics committee in accordance with the local committee requirements.

All adverse events must be recorded on the e-CRF with the following information:

1. the severity grade (mild, moderate, severe)
2. its relationship to the study drug(s) (see section 8.2)
3. its duration (start and end dates or if continuing at final exam)
4. whether it constitutes a serious adverse event (SAE)

- All adverse events recorded at any time after baseline on the CRF will be summarized at analysis.

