APPENDIX 08 – e-Delivery

Confidential

PIP-SICKLE

Page 1

Delivery

Record ID

Pregnancy Outcome	Miscarriage
	Pre-term Delivery
	 Term Delivery

Date of Miscarriage / Delivery

Gestation Age at Miscarriage / Delivery

(weeks)

(days)

BABY'S CONDITION AT BIRTH

Foetal Outcome	Alive
	Still Born
	Early Neonatal Death - Within 7 days of birth
	NNU Admission after 24 hrs Initial Observation
	Congenital Abnormality

Indication for Admission / Diagnosis

Congenital Abnormality

(Describe or Diagnosis)

Baby's Birth Weight

(g)

Head Circumference

(cm - 2 decimal places)

Baby's Length

(cm - 2 decimal places)

Confidential

Page 2

Apgar Score

(at 1 minute)

(at 5 minutes)

(at 10 minutes)

MATERNAL CONDITION AT MISCARRIAGE / DELIVERY

Maternal Complications

Pre-Eclampsia

Eclampsia

Sepsis

Pneumonia

Sickle Cell Crisis

Maternal Death

Others

Others

(Specify)

Sickle Cell Crisis

Vaso-occlusive

Haemolytic

Sequestration

Acute Chest Syndrome (ACS)

Severe Anaemia

Others

Others

(Specify)

Estimated Blood Loss

< 500 ml

500 - 1000 ml

> 1000 ml

Mother Physical Examination Within 1 Hour of Delivery

Maternal Weight

(kg - 2 Decimal Places)

Confidential

Page 3

BP

(Systolic)

(Diastolic)

Pulse Rate

Pulse Oximetry (SpO2)

Respiratory Rate

Temperature

LABORATORY

Haemoglobin Level

(At Today Visit)

Urinalysis Today

Leukocyte

- ± + ++

+++

Nitrite

- ± +

Urobilinogen

Negative Positive

Protein

- ± + ++

+++ +++++

Random Urine Sample Sent for UPCR

Yes No

pH

Blood		Negative	Positive
			
Specific Gravity			
Ketones		Negative	Positive
			
Bilirubin		Negative	Positive
			

08-06-2020 2:58pm

Powered by REDCap

Confidential

Page 4

Full Blood Count

Sample Taken for FBC

 Yes No

PCV

_____ (%)

Haemoglobin

_____ (g/dl)

Total WBC

_____ (cells/ml)

Neutrophils

_____ (%)

Lymphocytes

_____ (%)

Basophils

_____ (%)

Eosinophils

Monocytes

(%)

Platelet Count

(cells/ml)

Full Blood Count Result

Name of Clinician

CONFIDENTIAL

CONFIDENTIAL

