2.2 Endpoints

Primary

1. IUGR, perinatal death or miscarriage as a composite outcome

The occurrence of either IUGR, perinatal death or miscarriage will be the primary outcome.

IUGR will be defined as birthweight <10th centile for gestational age on the INTERGROWTH-21st birthweight charts, which is based on a healthy reference cohort from multiple countries, including Kenya(16). IUGR based on the Oken charts from a US national reference(17) maybe presented in sensitivity. A perinatal death refers to the death of a fetus after the age of viability (≥ 28 weeks' EGA), at delivery, or within the first week of life. A miscarriage refers to pregnancy, loss the death of a fetus before the age of viability (< 28 weeks' EGA). All participants will do an ultrasound scan at 20 weeks to estimate the gestational age of the pregnancy. Analysis will be by intention to treat.

Hypothesis:

1. We expect a 50% lower incidence of IUGR, perinatal death or miscarriage in the LDA (intervention) group compared to the placebo (control) group.

Secondary

1. The incidence of preeclampsia. Preeclampsia will be diagnosed based on ISSHP classification(18) if there is development of hypertension (either systolic blood pressure ≥ 140 mm Hg or diastolic blood pressure ≥ 90 mm Hg on two occasions at least 4 h apart) after 20 weeks gestation plus one of the following: proteinuria, thrombocytopenia, or any multisystem complication. Proteinuria will be defined as a dipstick test with 1+ proteinuria (≥ 30 mg dl $^{-1}$) on two occasions at least 4 hours apart, without any evidence of a urinary tract infection, or 2+ proteinuria or more on dipstick, or urinary protein creatinine ration >300 mg/g. Thrombocytopenia will be defined as a platelet count of $<100,000$ mm $^{-3}$.
2. The incidence of preterm delivery, defined as delivery at <37 weeks' EGA.
3. The incidence of:
 - a. Maternal death
 - b. Perinatal death
4. Number of sickle cell crises
5. Need for blood transfusion – identified based on whether the participant received a blood transfusion or not
6. Incidence of complications such as:
 - a. Urinary tract infection (UTI),
 - b. Lower Respiratory Tract Infection,
 - c. Acute chest syndrome,
 - d. retained placenta,
 - e. placental abruption; and
7. Incidence of potential adverse effects such as:
 - a. vaginal bleeding,
 - b. epigastric pain, and
 - c. heartburn

Analysis will be by intention to treat.

3 Study Methods

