8.1 Adverse events

This analysis will be conducted in the ITT population. The number and proportion of participants with adverse events that occur in up to 0.5% of the study population will be presented by the study arm.

Adverse events categorized by the treating physician to be related to the treatment will also be listed by the study arm, regardless of their frequency. These will include, but are not limited to, vaginal bleeding, epigastric pain, and heartburn.

Table shell 5. Adverse events

Adverse events	LDA, n(%)	Placebo, n(%)	Overall
Total			
Listed			

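### Vaginal bleeding and heartburn are secondary endpoints that no visit procedure prompts for, and the SAP sets out no clear by-arm comparison of the three named side effects regardless of attribution

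*Protocol*

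**What the plan says.** **Endpoints.** The secondary outcomes in Protocol 3.9 include "potential adverse effects such as vaginal bleeding, epigastric pain and heartburn". SAP 2.2, secondary item 7, lists the same three under "Incidence of potential adverse effects such as", with no condition on causality, and places them under intention to treat. Vaginal bleeding also appears in the second specific objective of both documents (Protocol 2.2, SAP 2.1).

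**Capture.** Protocol 8.1 begins its visit list with "The occurrence of adverse events, such as weakness, chills/rigors, headache, myalgia, dizziness, epigastric pain, abdominal pain, anorexia, nausea, vomiting, diarrhea" and ends it with "pruritus, coughing, tinnitus, abnormal gait, tremor, clonus or dyskinesia, will be sought by the investigator (or designee) at each study visit". The same section has signs and symptoms assessed at all follow-up visits and adds that "Adverse events also may be detected when they are volunteered by the patient during or between visits". The follow-up e-CRF (Protocol Appendix 07) records adverse events as free-text descriptions.

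**Analysis.** Protocol 8.3 states that "All adverse events recorded at any time after baseline on the CRF will be summarized at analysis". SAP 8.1 has two rules. The first presents events by arm according to a 0.5% frequency threshold, without regard to causality. The second reads "Adverse events categorized by the treating physician to be related to the treatment will also be listed by the study arm", whatever the frequency, and then names the three endpoints as among those events. SAP 7.2.2 gives relative risks with 95% confidence intervals for secondary endpoints but names none of the three, and neither does Table shell 3.

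**Delivery.** The delivery e-CRF (Protocol Appendix 08) has a field "Estimated Blood Loss" in three bands: under 500, 500 to 1000 and over 1000 ml. Neither document plans an analysis of it.

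**The concern.** The protocol sets out to evaluate safety and tolerability as well as efficacy, and it singles out three side effects as endpoints. One of them is among the symptoms that staff are told to look for at each visit. The other two are not, and no form field makes up for the omission. How often they are recorded may therefore depend on site habit and on what the woman chooses to mention.

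The analysis plan adds a second uncertainty. An endpoint defined as plain incidence needs a count by arm that does not depend on anyone's view of cause. The only SAP analysis text that names these endpoints ties them to events judged related, and the other rule that might catch them is worded so that its scope is unclear.

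At stake is how a finding of no difference in bleeding would be read. If few events are recorded or shown, such a result could be taken as reassurance when the trial had little ability to see a difference.

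**Working it through.** The plan gives no rate, power or precision for these endpoints, so there is no figure to reproduce. The check has three parts.

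**1. The three endpoints followed through the documents**

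| Place | Vaginal bleeding | Epigastric pain | Heartburn |
|---|---|---|---|
| Protocol 3.9, SAP 2.2 item 7 | endpoint | endpoint | endpoint |
| Protocol 8.1, symptoms sought at each visit (20 examples) | absent | listed | absent |
| Follow-up e-CRF, dedicated item | none | none | none |
| SAP 7.2.2 text and Table shell 3 | not named | not named | not named |
| SAP 8.1 | with related events | with related events | with related events |

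No other bleeding symptom is on the 8.1 list. Table shell 5, which serves SAP 8.1, has n (%) columns and no effect estimate.

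**2. The frequency rule in SAP 8.1**

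Input: 476 women (Protocol 3.2).

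- 0.005 × 476 = 2.38 women.
- 2/476 = 0.42% lies below the threshold; 3/476 = 0.63% lies above it.
- Literal reading (the threshold is a ceiling): the rule shows events seen in 1 or 2 women. An event seen in 3 or more appears only if judged related, which conflicts with Protocol 8.3.
- If a floor was meant: every event seen in 3 or more women is shown whatever its cause, and the relatedness rule matters only for events in 1 or 2 women.

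How much the relatedness judgement removes therefore depends on which reading was intended.

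**3. What incomplete capture would do**

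Let p0 and p1 be the true risks on placebo and aspirin, and c the share of events recorded, taken as equal in both arms because the trial is double blind.

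- Recorded risk ratio = (c × p1)/(c × p0) = p1/p0, unchanged.
- Recorded risk difference = c × (p1 − p0), reduced in proportion to c.
- Power = Φ{[d − 1.96 × √(2q(1 − q)/n)] / √[(a(1 − a) + b(1 − b))/n]}, where a and b are the recorded risks, d their difference, q their mean and n = 238 per arm (Protocol 3.2), at two-sided 5%.

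Example with assumed risks of 5% and 10%:

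- Full capture: (0.050 − 1.96 × 0.02414)/0.02404 = 0.11, so power is 54%.
- Half capture (2.5% and 5%): (0.025 − 1.96 × 0.01742)/0.01738 = −0.53, so power is 30%.

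The rates and capture shares below are all assumptions; the documents supply none.

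| Assumed risk, placebo / aspirin | Capture | Expected events | Risk difference (points) | Power |
|---|---|---|---|---|
| 3% / 6% | full | 7.1 / 14.3 | 3.0 | 35% |
| 3% / 6% | half | 3.6 / 7.1 | 1.5 | 20% |
| 5% / 7.5% | full | 11.9 / 17.9 | 2.5 | 20% |
| 5% / 7.5% | half | 6.0 / 8.9 | 1.25 | 12% |
| 5% / 10% | full | 11.9 / 23.8 | 5.0 | 54% |
| 5% / 10% | half | 6.0 / 11.9 | 2.5 | 30% |
| 10% / 20% | full | 23.8 / 47.6 | 10.0 | 87% |
| 10% / 20% | half | 11.9 / 23.8 | 5.0 | 54% |

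The direction is the same throughout. Power is often modest even with full capture.

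**The case against.** The sponsor has good answers to a stronger version of this point.

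- **The list is only illustrative.** Protocol 8.1 also has signs and symptoms assessed at every follow-up visit, and Protocol 8.3 has all reported or observed events documented whatever their severity or cause. Heavy or persistent vaginal bleeding is a reason to stop study drug (Protocol 7.7), so sites must be alert to it. This stands: capture is not absent. But the stopping rule concerns the severe end, whereas the endpoint is any vaginal bleeding, and nothing tells sites to ask about the two missing symptoms.
- **The form treats all three alike.** Epigastric pain has no tick-box either. This also stands, so the difference in prompting lies in the protocol text alone.
- **The relatedness list is an addition.** A reader might infer that the three endpoints are reported only if judged related. The documents do not support that: SAP 8.1 also has the frequency rule, SAP 2.2 defines plain incidence, and Protocol 8.3 summarises every recorded event. The category of possible relation in Protocol 8.2 is also broad, although SAP 8.1 does not say which categories count as related.
- **SAP 7.2.2 may already cover them.** Its endpoint list is not exhaustive, and Table shell 3 also leaves out retained placenta and placental abruption. One can argue that relative risks are promised for all secondary endpoints. What remains is that SAP 2.2, 7.2.2 and 8.1 do not agree and leave the analyst to choose.
- **Delivery blood loss is an endpoint in neither document**, and study drug ends at 36 weeks or delivery, so it is often measured off drug. A descriptive table would be useful, but its absence is not a fault in measuring harm.

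**Conclusion.** The point holds as a gap in prompting and in specification. Two of the three named side-effect endpoints are not systematically sought, and the SAP does not clearly set out a by-arm comparison of all three regardless of attribution. The literal 0.5% rule adds a conflict with Protocol 8.3.

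Two stronger conclusions are tempting. One is that harm is under-measured as a matter of fact. That is a reasonable inference but is not demonstrated, since sites may ask anyway and the documents hold no event rates. The other is that the plan is biased towards finding no excess bleeding. Under blinding, equal under-capture leaves the risk ratio unchanged; it lowers counts, understates absolute risks and costs power.

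The size is unknown. For a doubling of risk from assumed placebo rates of 3% to 10%, recording half the events lowers power by 15 to 33 percentage points (35% to 20%, and 87% to 54%). This rests on assumed rates, equal capture in the arms and 238 women per arm. The improvement is worth making because it is cheap; the primary analysis is not affected.

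**What to change.** **Protocol and forms.** Add vaginal bleeding and heartburn to the symptoms sought in Protocol 8.1 and keep every item already there. Add yes/no items for the three endpoints to the follow-up e-CRF. If enrolment has ended, state in the report that these two were not prompted.

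**SAP.** Tabulate all three endpoints by arm whatever the attribution, with a risk ratio or risk difference and 95% confidence interval, for example as rows in Table shell 3. Bring SAP 2.2, 7.2.2 and 8.1 into line with one another and with Protocol 8.3. Reword the 0.5% rule in SAP 8.1 so that it states the intended threshold. A separate list of related events can stay as a supplement.

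**Optional.** Show the three blood-loss bands by arm as a descriptive safety table, with a note on when study drug stops.

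**Cost.** One sentence in the protocol, three form items and a few table rows. Visits become slightly longer, and items added during the trial cover only later visits, so the report should separate prompted from unprompted periods. The SAP changes need no new data and should be made before unblinding.
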